We will use a three group randomized design in 150 older (60-85 years), obese (BMI=30-40 kg/m² or BMI= 27.0-<30 kg/m² plus one risk factor), men and women who will undergo a 12 month WL intervention to test our overall hypothesis that weighted vest use added to WL will better preserve bone health compared to WL alone and similarly to WL plus a structured RT intervention. All groups will receive the same WL intervention (caloric restriction targeting 10% WL and with adequate calcium, vitamin D, and protein intake), in accordance with national obesity treatment guidelines.⁶⁵ Thus, treatment groups are: WL alone (**WL**; n=50); WL plus weighted vest use (**WL+VEST**; targeting 8 hours/d, weight replacement titrated up to 10% WL; n=50); or, WL plus structured RT (**WL+RT**; targeting 3 sessions/week; n=50); **Table 1.** All outcome assessments occur at baseline, six, and 12 months.

Table 1. Proposed Intervention Components by Treatment Group.

Intervention Components	Intensive WL Phase (Months 1-6)	Reduced Contact WL Phase (Months 7-12)
Weight Loss (WL)	Weekly behavioral-based group sessions; 10% WL goal following national obesity treatment guidelines	Biweekly behavioral-based group sessions; 10% WL goal following national obesity treatment guidelines
WL + Weighted Vest (WL+VEST)	WL + 8 hours/day weighted vest use titrated weekly to adjust for achieved WL (up to 10% baseline weight)	WL + 8 hours/day weighted vest use titrated biweekly to adjust for achieved WL (up to 10% baseline weight)
WL + Resistance Training (WL+RT)	WL + 3 days/week progressive, structured RT	

Recruitment of study participants: Randomization of 150 participants will ensure at least 85% statistical power (with a conservative drop-out rate of ~15%; n=128 completed) to detect significance between group differences in our primary outcome (12 month total hip trabecular vBMD). We plan to recruit, screen and enroll during Years 1-3.5 of the study. We will target older adults who live in the area via media advertisements and mass mailings.

Participant screening and randomization

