Weight Loss + Weighted Vest Intervention (WL+VEST). The WL component of the intervention is described above. Participants assigned to the WL+VEST group will each receive an appropriately-sized weighted vest for the duration of the 12 month intervention. The vest fabric and design fits comfortably over or under clothing (individual weights are $\frac{1}{4}$ inch thick), allows for full range of motion and movement, and full chest expansion without restricting breathing. An unloaded vest weighs about one pound and is available in several sizes, including XXL. The vest firmly and evenly distributes weight over the body's core when the small (about the size of a domino piece) 2.25 oz weight blocks are added into the vest pockets. Participants in this group will be asked to wear the vest on a daily basis, progressing to a goal of 8 hours/day (by week 2) during their most active part of the day. Initially, the vest will be unloaded (e.g., one-pound vest only without added blocks). The vest weight will then be incremented according to each participant's rate of WL based on their weekly (first 6 months) and biweekly (final 6 months) body weight assessments. As body mass is lost, the weight of the vest will be increased (with the 2.25 oz weight blocks) to replace the lost weight. The goal is to maintain the

gravitational loading on the musculoskeletal system throughout the intervention by replacing lost body mass via external loading. To objectively monitor wear time, intervention staff will periodically embed a small accelerometer into one of the vest pockets during the weekly/biweekly group sessions. These devices collect accelerations across the X, Y, and Z axes and conventional wear-time algorithms will be applied to identify periods of non-wear time of the vest. Participants will also keep a daily log to record the time worn, vest weight, and any complications or comments related to the vest use, with overall satisfaction of vest use assessed at study close. Intervention staff will monitor and discuss accelerometer output and daily logs at the end of each group session, intervening to enhance compliance to the vest protocol when necessary.

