Statistical Analyses. We will use intention-to-treat principles in full accordance with CONSORT guidelines. We will monitor serious adverse events regularly to maintain up-to-date safety information for reporting to the DSMB. All data will undergo range checks at the time of data entry and will be examined monthly by histograms and bivariate scatterplots to check for inconsistencies, unusual data needing further verification, and outliers. Plots of longitudinal observations will be used to inspect for unusual changes requiring verification against source documentation. Regression diagnostics and exploratory analyses will be performed to find appropriate transformations of variables if needed. Order of priority in choosing a transformation will be to satisfy: 1) linearity, 2) homogeneity, and 3) normality assumptions. We will attempt to identify baseline covariates that predict attrition and compliance; and if such covariates can be identified, the analyses may need to incorporate stratification by these factors to decrease bias. In addition, following the recommendations of the 2010 National Academy of Sciences report,¹¹⁰ if the outcome is found to be missing at random, we will attempt to identify baseline covariates that predict attrition and use these covariates to impute missing data based on multiple imputation. Sensitivity analyses, using methods like pattern mixture models, will be carried out to explore the effect of missing outcomes on inference (if found to be not at random). Additionally, we will conduct sensitivity analyses of efficacy taking into account treatment compliance as a binary (compliers defined as >80% of prescribed vest wear time, >80% resistance training attendance, >80% of weight loss target) or continuous variable (proportion of treatment received).

Sample Size and Power. A total sample size of 150 (n=50 per group) is optimal to test hypotheses for the primary study aims. Using co-primary hypotheses demands use of a conservative Bonferroni correction of dividing the Type I error rate (α) in half for each aim to determine statistical significance.

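### The binary vest-complier rule in the compliance sensitivity analysis scores wear time only and ignores the titrated load, so full hours in an under-loaded vest count as compliance.

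*Combined protocol and SAP*

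**What the plan says.** Methods and Measures gives the vest arm two targets: "targeting 8 hours/d, weight replacement titrated up to 10% WL". Table 1 repeats the daily hours and says the vest is titrated weekly, then biweekly, "to adjust for achieved WL (up to 10% baseline weight". The WL+VEST section under Study Interventions describes the mechanics: "As body mass is lost, the weight of the vest will be increased (with the 2.25 oz weight blocks) to replace the lost weight". It gives the purpose as keeping gravitational loading constant by replacing lost mass externally.

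The Statistical Analyses section plans sensitivity analyses of efficacy that account for compliance. The binary form has "compliers defined as >80% of prescribed vest wear time, >80% resistance training attendance, >80% of weight loss target". The alternative is "or continuous variable (proportion of treatment received"), with no statement of what that proportion counts for the vest.

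Three monitoring provisions in the WL+VEST section bear on this. For the accelerometer placed periodically in the vest, "conventional wear-time algorithms will be applied to identify periods of non-wear time of the vest". On self-report, "Participants will also keep a daily log to record the time worn, vest weight, and any complications". On oversight, "Intervention staff will monitor and discuss accelerometer output and daily logs at the end of each group session", with action to improve compliance where needed.

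**The concern.** Load is the active ingredient of the vest, and hours are how long it is applied. A rule that scores only hours cannot tell a correctly loaded vest from a nearly empty one.

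The compliance analysis is the planned efficacy analysis that takes received treatment into account. If WL+VEST compliers show a weak effect on total hip trabecular vBMD, there are two explanations: external loading does not protect bone, or the load was not carried. With under-loaded participants inside the complier group, the binary analysis cannot separate them. The reading of a disappointing vest result is what is at stake. The trial's primary conclusions are not.

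**Working it through.** The plan gives no figure to reproduce here. The check sets the prescription against the rule and then illustrates the gap.

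**1. Does any stated criterion test the load carried?**
- Vest criterion: hours only.
- Weight-loss criterion: if it also applies to the vest arm, more than 80% of a 10% target means a loss above 8% of baseline weight. That sets the load that should be carried, not the load that was.
- Accelerometer: wear and non-wear only.
- Daily log: vest weight is recorded, but no stated analysis uses it.

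**2. One day.** Inputs: 100 kg person with a 10 kg loss (the protocol's own example in the Weight Loss Intervention section); 8 hours a day; empty vest of about one pound (0.454 kg).
- Prescribed: 10 kg × 8 h = 80 kg-h.
- Half load, full hours: 5 kg × 8 h = 40 kg-h; 40/80 = 50%.
- Empty vest, full hours: 0.454/10 = 4.5%.
- Hours are 100% in both cases, and weight loss is 10/10 = 100% of target. Both people are compliers.

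**3. Twelve months (illustration).** Assumptions, not documented facts: linear loss to 10 kg at week T, then held; the vest follows the loss up to 5 kg and no more blocks are added; 8 hours worn every day.
- Prescribed load P(t) = min(10t/T, 10) kg, at least 0.454 kg. Delivered load D(t) = min(P(t), 5).
- Without the floor, over 52 weeks, the sum of P is 520 − 5T and the sum of D is 260 − 1.25T kg-weeks. The floor adds the same small area to both: 0.5 × 0.454 × (0.454T/10), which is 0.27, 0.40 and 0.54 for T = 26, 39 and 52.
- The mean of D/P over time is [T/2 + (T/2) ln 2 + (52 − T)/2]/52.

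| T (weeks) | Sum D / sum P | Ratio of means | Mean of ratios | Hours |
|---|---|---|---|---|
| 26 | 227.77/390.27 | 58.4% | 67.3% | 100% |
| 39 | 211.65/325.40 | 65.0% | 76.0% | 100% |
| 52 | 195.54/260.54 | 75.1% | 84.7% | 100% |

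All three are compliers under the written rule. None passes an 80% load threshold taken as a ratio of means. The T = 52 case passes if interval ratios are averaged, so the averaging rule has to be stated. An always-empty vest with T = 26 delivers 0.454 × 52 / 390.27 = 6% of the year's prescribed load and still meets the vest criterion.

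**4. Handling of missing log days.** Suppose T = 26, the vest is at 70% of prescribed load throughout, and nothing is logged in weeks 0 to 10.
- Hours, with missing days as zero: 42/52 = 81%, which passes.
- Mean prescribed load over weeks 10 to 52: [16 × (3.85 + 10)/2 + 26 × 10]/42 = 8.83 kg. Over the full year: 390/52 = 7.5 kg.
- Logged mean over the full-year prescribed mean: 0.70 × 8.83/7.5 = 82%, a false pass.
- Both means over the same logged days: 0.70 × 8.83/8.83 = 70%, a correct fail.

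A load criterion therefore needs both means taken over the same days.

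**The case against.** The case for leaving the rule alone is substantial. Only a sensitivity analysis is affected. Staff tie vest weight to weekly or biweekly weigh-ins and review logs that include vest weight, so under-loading may be uncommon. Hours are the vest component with an objective check, while load rests on self-report. The other arms also use simple criteria: resistance-training compliance is attendance only, although that prescription includes sets and 70–75% of 1RM. The continuous measure could be read as including load. The limb-loading sub-study measures foot-contact forces and correlates them with BMD change, so the plan does not ignore delivered load.

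These points limit the importance of the matter, and the comparability argument is a good reason to keep the hours-only version. They do not change how the binary rule classifies anyone. Log review is not part of the rule. The continuous measure is undefined for the vest. The sub-study has 15 participants per group and 4 days of insole wear, and it does not reclassify compliers.

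A reader might go further and infer that under-loading is common, or that 58–75% is the dose to expect. The documents give no under-loading rate, and those figures come from an assumed 5 kg cap.

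**Conclusion.** The point holds for the binary vest criterion: it omits one of the two prescribed components, so a full-hours, under-loaded wearer is scored as a complier. This follows from the text and needs no assumption. How many participants it would misclassify cannot be estimated from the documents. The 50% figure is the protocol's own example at an assumed half load; the 12-month figures rest on the assumptions stated with them.

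It would be tempting to infer that the vest comparisons themselves are compromised. The documents do not support that. The co-primary tests follow intention to treat and use no compliance variable, so their validity, alpha and planned power are untouched. Nor do the documents show that the continuous measure ignores load; they leave it open. This is a cheap improvement to a sensitivity analysis, worth making before the data are examined.

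**What to change.** In the Statistical Analyses section:

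1. Keep the hours-only vest definition, and use it when WL+VEST and WL+RT complier results are compared.
2. Add a load-based definition: more than 80% of prescribed wear time **and** mean logged vest weight above 80% of mean prescribed load. Take both means over the same logged days, as a ratio of means. Credit logged weight only up to the prescribed load, so that over-loading at one time cannot offset under-loading at another.
3. Define prescribed load as the loss at the most recent available weigh-in, carried forward if a session is missed, with the empty vest as minimum and 10% of baseline weight as maximum. Where vest goals are reduced or suspended for injury or symptoms (Safety measures during the interventions), substitute the load or hours that staff set, so that a participant following medical advice is not scored as a non-complier.
4. State that the vest arm's continuous measure is delivered over prescribed load-hours.
5. Count missing log days as zero hours, and repeat the analysis with those days excluded.
6. Report both binary versions.

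The cost is a few sentences and some programming of log data before database lock. No new data, visits or participants are needed, because time worn and vest weight are already logged daily. The downsides are that load is self-reported and that the load-based version is stricter than attendance-only resistance-training compliance.

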Aim 1, Hypothesis 1. Based on our preliminary data demonstrating effectiveness of the WL+VEST intervention in preserving total hip abMD, as well as effect size estimates generated from an 18 month trial of WL versus WL+RT on total hip vBMD, we anticipate that the WL+VEST group will decrease 3% from a baseline total hip vBMD value of 0.300 g/cm³ over 12 months compared to 5.5-6.0% decrease in the WL alone group, leading to a difference range of 2.5-3.0%. In **Table 4**, we observe that assuming 12 month group differences in total hip vBMD between 0.0075 and 0.009 g/cm³, we have at least 85% power to detect a statistically significant difference for the primary outcome assuming common group standard deviations of 0.010 g/cm³ and using a 2-sided t-test under differing retention scenarios over 12 months at a

Table 4. Power for Aim 1, Hypothesis 1.

12 Month Δ Total Hip vBMD g/cm ³ : WL+VEST (Δ %)	12 Month Δ Total Hip vBMD g/cm ³ : WL (Δ %)	12 Month Attrition		
		15%	13%	10%
		Power (%)*		
-0.009 (-3.0%)	-0.0165 (-5.5%)	87.7	88.6	89.7
-0.009 (-3.0%)	-0.018 (-6.0%)	96.7	97.1	97.5

* Assumes n=50/group and unadjusted SD=0.010 g/cm³ and $\alpha=0.025$ under 2-sided alternative hypothesis.

0.025 level of significance. Although we do not have pilot data specifically assessing total hip trabecular vBMD (only total hip vBMD, which is an integral measure of the trabecular and cortical regions), the two are highly correlated, with prior studies showing enhanced responsivity of the trabecular region.^{111,112} Thus, using total hip vBMD for our power calculations ensures adequate power for total hip trabecular vBMD as the primary outcome measure.

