Aim 1, Hypothesis 2. We anticipate that the change in total hip trabecular vBMD among the WL+VEST will be noninferior to the change among WL+RT. The noninferiority margin for the difference in 12-month total hip vBMD changes is -4% of baseline or -0.012 g/cm³, as used previously.¹¹³ Assuming 12-month equivalence between WL+VEST and WL+RT (i.e., WL+VEST and WL+RT 12 month mean are each 0.291 g/cm³), then a baseline sample size of 50/group provides >95% power to establish noninferiority of WL+VEST compared to WL+RT. This assumes 1) the same SD of change (0.010 g/cm³) as in Hypothesis 1; 2) attrition rate is a conservative 15% (better retention provides higher power); and 3) the Type I error rate is 0.0125, based on the convention of using 0.025 for a one-sided test, which is further divided in half due to having co-primary hypotheses.¹¹⁴ Alternately, using a smaller noninferiority bound provides a stricter standard for the trial objectives. Using a margin of -2.5% of baseline (-0.0075 g/cm³) difference between WL+VEST vs WL+RT, we have 85% power to establish noninferiority assuming the same SD as above (0.010 g/cm³), 15% attrition, and a 0.0125 Type I error rate.

Aim 2, Hypothesis 1. We note that the CT estimates were partially derived from DXA-measured aBMD loss under WL, which results in similar estimated BMD losses assumed between the two groups. We anticipate that the WL+VEST group will decrease 3% from a baseline total hip aBMD value of 1.027 g/cm² over 12 months compared to 5.5% decrease in the WL alone group, leading to a difference of 0.0257 g/cm², or 2.5% of baseline. Using this magnitude of difference, 50 participants/group will provide 90% power to detect a statistically significant difference for the primary outcome assuming common group standard deviation of change of 0.033 g/cm², based on a 2-sided t-test under 85% retention at 12 months using a 0.025 Type I Error rate.

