Aim 2, Hypothesis 2. We anticipate that the change in total hip aBMD among the WL+VEST will be noninferior to the change among WL+RT. The noninferiority margin (i.e. difference at which a clinically meaningful increase of nonvertebral fracture risk may occur¹¹⁵) for the difference in 12 month total hip aBMD changes is -2.13% of baseline or -0.022 g/cm². Assuming equivalence between WL+VEST and WL+RT (i.e., WL+VEST and WL+RT 12 month mean are each 3% reduced from baseline (0.996 g/cm²) as used in Hypothesis 1), then a baseline sample size of 50/group provides 80% power to establish noninferiority of WL+VEST compared to WL+RT such that the lower bound of the one-sided 0.9875 confidence bound of the group mean differences will be greater than a -0.022 g/cm² difference between WL+VEST minus WL+RT. This assumes 1) the same common group SD of change (0.033 g/cm²) as in Hypothesis 1; 2) attrition rate is 15%; and 3) the Type I error rate is 0.0125, based on the convention of using 0.025 for a one-sided confidence interval, which is further divided in half due to having co-primary hypotheses.

Aim 2, All other outcomes. Due to the challenges of prespecifying noninferiority boundaries for exploratory outcomes, all other analyses for the second aim will focus on the three group comparisons of WL, WL+VEST, and WL+RT. Based on the same baseline sample size of 50/group (n=150 overall), we will have 80% power to detect a relatively modest effect sizes (variance of means/within-group variance) of 0.116 under the attrition rate of 15% assumed above, assuming 2-tailed F-test and a 0.05 Type I error rate.

Statistical Analysis Plan. The primary aim for comparisons of total hip trabecular vBMD will be tested using a mixed model fit using the change in total hip trabecular vBMD at 12 months versus the treatment effect indicator for each of the three groups, adjusted for visit (6 or 12 months), visit by treatment interaction, sex (to account for randomization strata) and baseline value. A contrast statement will test change in total hip trabecular vBMD at 12 months in WL versus WL+VEST, and a statistically significant difference will be

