established at $p<0.025$. Next, the noninferiority of WL+VEST compared to WL+RT will be determined based on whether the lower bound of the one-sided confidence interval for the estimated 12 month treatment effect of WL+VEST versus WL+RT overlaps the -4.0% non-inferiority boundary for total hip trabecular vBMD. This will be performed using $\alpha=0.0125$ to account for co-primary hypotheses as well as for using a 1-sided alternative hypothesis. Tests for both co-primary hypotheses will be based on different contrast statements from the same statistical model. Secondarily, we will repeat these analyses with the short-term effect at 6 months of both interventions as an exploratory analysis. For Aim 2, we will repeat these analyses for the 12 month effect (and secondarily 6 month effect) using total hip aBMD assessed by DXA as the outcome. Comparisons will be performed for both superiority of WL+VEST vs. WL as well as noninferiority of WL+VEST vs WL+RT based on a 2.13% noninferiority margin using the methods described above. Analytic models for all other Aim 2 outcomes will mirror the model used in the primary aim, with the important exception that comparisons will focus on statistical comparisons of group mean differences. All outcomes are assessed at 6 and 12 months, and while both visit time points will be estimated, the 12 month treatment effect will be considered of primary interest. Treatment effects for changes in outcome variables are compared using a mixed model fit with treatment group, visit, and treatment by visit interaction, adjusted for sex and baseline values of the outcome. Tests will be performed using contrast statements at 12 months (primarily) and 6 months (secondarily), and we will use the partial F-test $p<0.05$ for significance. Significant comparisons for secondary outcomes will further use comparisons of all three groups at each visit using $p<0.0167$ for pairwise significance. Lastly, we intend to explore the associations between 6 and 12 month change in vBMD or aBMD with change in secondary outcome measures (i.e., DXA and CT-acquired body composition, D3Cr muscle mass, biomarkers of bone turnover, bone regulating hormones/cytokines) using linear regression methods and adjusted for sex and treatment group, to explore potential mechanisms underlying the treatment effect. Secondary comparisons will not be adjusted for multiplicity other than for pairwise group comparisons. Statistical analyses will be conducted using SAS v9.4 (SAS Institute, Cary, NC) and R software.

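### Fixed Bonferroni levels are valid but not required: Holm's step-down rule keeps the family-wise limit at 5% and lifts Hypothesis 1 power from about 88% to 93% in the plan's 2.5% case

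*Combined protocol and SAP*

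**What the plan says.** The opening of Sample Size and Power treats the correction as compulsory: "Using co-primary hypotheses demands use of a conservative Bonferroni correction of dividing the Type I error rate (α) in half for each aim". The later text carries this through as two fixed levels.

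- **Hypothesis 1 (superiority of WL+VEST over WL).** Aim 1, Hypothesis 1 bases power on "using a 2-sided t-test under differing retention scenarios over 12 months at a" level of 0.025, and the Statistical Analysis Plan section declares significance at p<0.025. The Table 4 footnote reads "Assumes n=50/group and unadjusted SD=0.010 g/cm³". At 15% attrition the table gives 87.7% power for a difference of 0.0075 g/cm³ (2.5% of baseline) and 96.7% for 0.009 g/cm³ (3.0%).
- **Hypothesis 2 (non-inferiority of WL+VEST to WL+RT).** Aim 1, Hypothesis 2 sets a Type I error of 0.0125, explained as "using 0.025 for a one-sided test, which is further divided in half due to having co-primary hypotheses". The Statistical Analysis Plan section repeats the level, "to account for co-primary hypotheses as well as for using a 1-sided alternative hypothesis". The margin is -4% of baseline (-0.012 g/cm³), with over 95% power claimed if the two arms are equal. A stricter -2.5% margin (-0.0075 g/cm³) is also costed.
- **DXA pair.** Aim 2, Hypothesis 2 uses the same scheme through "the lower bound of the one-sided 0.9875 confidence bound of the group mean differences".

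Neither level depends on the other result, and no step-down or alpha-passing rule appears. The Statistical Analysis Plan section adds that "Tests for both co-primary hypotheses will be based on different contrast statements from the same statistical model".

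**The concern.** Because each hypothesis can be claimed alone, some multiplicity control is needed. Bonferroni supplies it, but so do other rules. Holm's procedure needs no further assumption, holds under any correlation (the two contrasts share the WL+VEST arm), and rejects everything that Bonferroni rejects.

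The fixed split is costly here because, on the plan's assumptions, Hypothesis 2 at the -4% margin is almost certain to succeed. The alpha set aside for it could then pass to Hypothesis 1, the direct test of whether the vest adds anything to diet alone.

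The spare power is worth having because the SD is uncertain. The plan says "Although we do not have pilot data specifically assessing total hip trabecular vBMD", so 0.010 g/cm³ comes from integral hip density, not from the actual primary outcome.

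**Working it through.** **Inputs, all from Sample Size and Power:** 50 randomised per arm; 15% attrition; SD 0.010 g/cm³; WL+VEST minus WL of 0.0075 or 0.009 g/cm³; margin 0.012 or 0.0075 g/cm³; WL+VEST equal to WL+RT.

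**Step 1. Reproduce the plan's figures.** With n = 50 × 0.85 = 42.5 per arm, the noncentrality is δ / (σ√(2/n)). For δ = 0.0075 this is 0.0075 / (0.010 × √(2/42.5)) = 3.457. At two-sided 0.025 on 83 df the critical value is 2.283.

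- δ = 0.0075: power 87.8% (Table 4: 87.7%).
- δ = 0.009: power 96.7% (Table 4: 96.7%).
- Hypothesis 2, margin 0.012, one-sided 0.0125: noncentrality 5.53, power 99.9% (plan: over 95%).

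**Step 2. Define Holm for this pair.** Let p1 be the two-sided p-value for Hypothesis 1 and p2 the one-sided p-value for Hypothesis 2. Compare p1 with 2 × p2. Test the smaller at 0.025. If it is rejected, test the other at 0.05, which for p2 means one-sided 0.025.

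**Step 3. Approximate the gain.** Hypothesis 2 passes in 99.9% of trials, so Hypothesis 1 is in effect tested at two-sided 0.05 (critical value 1.989). The t-test power becomes 92.7% for δ = 0.0075 and 98.4% for δ = 0.009.

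**Step 4. Simulate both rules.** One million trials per scenario, 42 per arm, shared WL+VEST arm, variance pooled over three arms (123 df). Hypothesis 1 power:

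| Scenario | Fixed levels | Holm |
|---|---|---|
| δ 0.0075, margin 4% | 87.7% | 92.6% |
| δ 0.009, margin 4% | 96.7% | 98.3% |
| δ 0.0075, margin 2.5% | 87.7% | 91.2% |
| δ 0.0075, margin 4%, RT better by 0.003 | 87.8% | 92.3% |
| δ 0.0075, margin 4%, RT better by 0.006 | 87.7% | 89.7% |
| δ 0.0075, margin 2.5%, RT better by 0.003 | 87.7% | 88.5% |
| δ 0.0075, margin 2.5%, RT better by 0.006 | 87.7% | 87.7% |
| δ 0.0075, margin 4%, SD 0.008 | 97.8% | 98.9% |
| δ 0.0075, margin 4%, SD 0.009 | 93.8% | 96.6% |
| δ 0.0075, margin 4%, SD 0.012 | 72.4% | 81.0% |

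The SDs other than 0.010, and the advantages for WL+RT, are assumed ranges that the plan does not give. With the 2.5% margin and equal arms, Hypothesis 2 also rises from 87.7% to 91.2%, and the chance of winning both rises from 80% to 87%. For the DXA pair (difference 0.0257, margin 0.022, SD 0.033 g/cm²), Hypothesis 1 goes from 90% to 92%, Hypothesis 2 from 78% to 84%, and both from 74% to 82%.

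**Step 5. Express the gain in participants.** At fixed two-sided 0.025, δ = 0.0075 and SD 0.010, reaching 92.6% takes 49.6 completers per arm. 49.6 / 0.85 = 58.4, so 58 to 59 randomised per arm instead of 50.

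**Step 6. Check the error rates (margin 4%).**

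| Truth | Error | Fixed | Holm |
|---|---|---|---|
| VEST = WL = RT (only the Hypothesis 1 null true) | Hypothesis 1 | 2.5% | 5.0% |
| VEST = WL = -5.5%, RT = -3% (only the Hypothesis 1 null true) | Hypothesis 1 | 2.5% | 3.7% |
| Only the Hypothesis 2 null true | Hypothesis 2 | 1.25% | 2.5% |
| Both nulls true | Either | 3.6% | 3.6% |

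None exceeds 5%.

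**The case against.** The strongest reply is that nothing is broken. Bonferroni is valid, Table 4 reproduces, the power target is met, and the authors themselves call the correction conservative. Several further points are true.

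- **More error is spent.** The plan never states 5% for the primary pair; it follows from halving to 0.025. The actual levels bound the family-wise error at 0.025 + 0.0125 = 3.75%. Holm can use the full 5%, and the Hypothesis 1 error doubles when the vest does nothing and all arms lose equally.
- **The gain leans on an easy Hypothesis 2.** The 0.012 margin is wider than the whole vest effect expected (0.0075 to 0.009). A useless vest (VEST = WL = -5.5%, RT = -3%) would still pass Hypothesis 2 about 42% of the time, and under Holm that pass relaxes Hypothesis 1. Fixed levels keep the two apart.
- **There may already be a reserve.** Table 4 uses an unadjusted SD, while the planned model adjusts for baseline and sex. If baseline correlated with change at 0.3 or 0.4 (assumed), fixed-level power would be about 91% or 93%. The plan also argues that the trabecular measure responds more strongly.
- **Reporting and timing.** The non-inferiority bound would have a level that depends on Hypothesis 1, and a mid-trial change could look opportunistic. The documents describe monthly data checks and do not mention blinding of analysts.

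These points bear on how large and how welcome the gain is. They do not make Bonferroni necessary, and Holm's power never falls below the fixed-level figure. A team may reasonably keep 0.025 as a safeguard, but that is a choice to be stated as one.

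**Conclusion.** The point holds as a cheap improvement and a correction of wording; it is not an error in the plan's inference. The statement that co-primary hypotheses require Bonferroni is inaccurate. On the plan's own assumptions, Holm adds about 5 percentage points to Hypothesis 1 power in the 2.5% case and about 1.6 points in the 3.0% case, without more participants. In the 2.5% case the risk of missing a real effect falls from about 12% to 7%.

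This size rests on the -4% margin, WL+VEST equal to WL+RT, SD 0.010 g/cm³ and 15% attrition. The gain is larger if the SD is larger (nearly 9 points at 0.012). It is smaller with the stricter margin or a better WL+RT arm, and nil when WL+RT is better by 0.006 g/cm³ under the 2.5% margin. Family-wise error stays within 5%, although more of that allowance is used than under the plan's present levels.

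**What to change.** Before any unblinded outcome data are seen, replace the fixed levels in Sample Size and Power and in the Statistical Analysis Plan section with Holm's rule:

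1. Compare the two-sided p-value for Hypothesis 1 with twice the one-sided p-value for Hypothesis 2.
2. Test the smaller at 0.025.
3. If it is rejected, test the other at 0.05.

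The one-sided confidence bound for non-inferiority is then 98.75%, or 97.5% once Hypothesis 1 has been rejected. State the 5% family-wise limit as a number. The same rule can serve the exploratory total hip aBMD pair.

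The cost is SAP text only, since both tests are already contrasts from one model. Three things are given up: simple simultaneous confidence intervals, a non-inferiority bound whose level is fixed in advance, and the 2.5% ceiling on the Hypothesis 1 error.

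If the team prefers that ceiling, or if unblinded results have already been seen, keep the fixed levels. In that case, drop the claim of necessity and say that Bonferroni was chosen, giving the actual reason.
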